Prospective, Randomized, Double-blinded,
Split-face Study Comparing Efficacy of Lidocaine
2.5%/Prilocaine 2.5% Cream Under Occlusion,
and Compounded Lidocaine 23% /Tetracaine
7% Ointment for Topical Anesthesia Prior to
1927 nm Fractional Thulium Fiber Laser
Treatment of the Face

NCT04523961

22February2021

IRB Minimal Risk Protocol Template

Note: If this study establishes a human specimen repository (biobank) for research purposes, do not use this template. Use the Mayo Clinic Human Specimen Repository Protocol Template found on the IRB home page under Forms and Procedures at <http://intranet.mayo.edu/charlie/irb/>

First-time Use: Use this template to describe your study for a new IRB submission.

1. Complete the questions that apply to your study.
2. Save an electronic copy of this protocol for future revisions.
3. When completing your IRBe application, you will be asked to upload this document to the protocol section.

Modification: To modify this document after your study has been approved:

1. Open your study in IRBe. Click on the study 'Documents' tab and select the most recent version of the protocol. Save it to your files.
2. Open the saved document and activate "Track Changes".
3. Revise the protocol template to reflect the modification points, save the template to your files
4. Create an IRBe Modification for the study and upload the revised protocol template.

General Study Information

Principal Investigator: [name]

Study Title: Prospective, randomized, double blinded, split-face study comparing efficacy of lidocaine 2.5%/ prilocaine 2.5% cream under occlusion and compounded lidocaine 23% / tetracaine 7% ointment for topical anesthesia prior to 1927 nm fractional thulium fiber laser treatment of the face

Protocol version number and date: 3, 2/22/2021

Research Question and Aims

Hypothesis: Does lidocaine 23% / tetracaine 7% ointment provide greater topical anesthetic compared to lidocaine 2.5%/ prilocaine 2.5% cream?

Aims, purpose, or objectives:

1. To compare the efficacy of lidocaine 23% / tetracaine 7% ointment and lidocaine 2.5%/ prilocaine 2.5% cream in reducing self-reported pain after laser treatment.
2. To determine the amount of burning and itching a patient experiences with lidocaine 23% / tetracaine 7% ointment compared to lidocaine 2.5%/ prilocaine 2.5% cream.
3. To determine if any symptoms of lidocaine toxicity occur during treatment visit (tinnitus, lightheadedness, diplopia, metallic taste in the mouth, slurred speech, localized muscle twitching, fine tremors).
4. To determine the amount of erythema on the face after application of both anesthetics.

Background (*Include relevant experience, gaps in current knowledge, preliminary data, etc.*):

Topical anesthetics are used commonly in outpatient dermatologic procedures. Applied topical anesthetics must transverse the epidermis and target the nerves in the dermis. Occlusion is one of several techniques that help with dermal absorption of the topical anesthetic¹. Topical anesthetic is not without risk. Signs and symptoms of lidocaine toxicity can start around blood lidocaine levels of 1-5 µg/mL and respiratory depression and/or coma at 20-25 µg/mL.

A commonly used FDA-approved medication for topical anesthetic is EMLA ® Cream, a eutectic mixture of lidocaine 2.5% and prilocaine 2.5%. EMLA ® Cream is applied to intact skin under occlusive dressing for at least 1 hour, with maximum dermal analgesia at 2-3 hours². The amount systemically absorbed is related to the surface area that it is applied and the duration of time applied. When applied to over 400 cm² for 24 hours, the peak blood levels of lidocaine was approximately 1/20 of the systemic toxic level and prilocaine was approximately 1/36 the toxic level.

Higher levels of lidocaine have also shown to be safe. A prospective study of lidocaine 30% was shown to be well tolerated with no adverse reaction when used on the face, neck, and chest with intense pulse light treatment³. In another study, 12 grams of 23% lidocaine/7% tetracaine ointment was applied to face for 2 hours, and the median peak lidocaine level was 1.15 µg/mL with no serious adverse effects. Twenty-one percent of patients reported a symptom of dizziness, drowsiness, lightheadedness, numbness or tingling, or back pain, and 90% of patients reported at least one cutaneous side effect⁴.

Absorption of lidocaine has been well studied². When applying 2.5% lidocaine to intact skin, 0.045 mg/cm² of lidocaine is absorbed per hour. At 12 times the strength, 30% lidocaine cream would then absorb 0.54 mg/cm²/hour. Assuming the full face was covered at 300 cm² for one hour, the total lidocaine absorbed would be 121.5 mg (0.54*300*1.0) would be 162 mg. The maximum recommended dose of lidocaine without epinephrine is 4.5 mg/kg or 300 mg. For example, a low weight patient (50 kg) patient would have a maximum of dose of 225 mg.

EMLA ® Cream is the only FDA approved topical anesthetic available for dermatologic outpatient procedures, however, use of other topical anesthetics is common and there is limited data comparing the efficacies. We aim to compare the efficacy of lidocaine 2.5%/prilocaine 2.5% cream under occlusion and compounded lidocaine 23% / tetracaine 7% ointment for topical anesthesia prior to 1927 nm fractional thulium fiber laser treatment of the face.

Study Design and Methods

Methods:

Lidocaine 23% / tetracaine 7% ointment and lidocaine 2.5%/ prilocaine 2.5% cream are both topical anesthetics that are used commonly by cosmetic dermatologists to numb the skin prior to laser procedures. We want to perform a prospective study evaluating the amount of pain (10 point VAS score for pain), burning, and itching that patients experience during the procedure. The targeted patients for accrual will be patients paying to undergo 1927 nm fractional thulium fiber laser treatment of the face for photodamage. Patients will be recruited between approval of IRB modification until we obtain target accrual, estimated to go until 12/2021.

Prior to the procedure, we will obtain consent from the patient to participate in the study. Lidocaine and tetracaine are pregnancy category B and thus pregnancy test is not needed if patients meet definitions described in inclusion criteria. Valacyclovir 500mg twice daily for 10 days will be given to all patients with a history of cold sores. We will randomly assign half of the face to be applied with 2.5 g of lidocaine 23% / tetracaine 7% ointment without occlusion and the other half of the face with 7.5 g lidocaine 2.5%/ prilocaine 2.5% cream with occlusion for 60 minutes compounded by Mayo Clinic Pharmacy. The topical anesthetics will only be applied to intact skin that is at least 1 cm away from the eyes. Lidocaine 2.5%/ prilocaine 2.5% cream will be applied to half the face by nursing staff and occluded. Lidocaine 23% / tetracaine 7% ointment will be applied to the other half of the face by the patient, given that it is their own outside prescription.

After 60 minutes we will remove the creams with soap and water, cleanse face with alcohol to ensure face is free of all moisture and water. Before the procedure, patients will take an electronic RedCap survey on an iPad to determine burning and itching on each side of the face. Physicians will assess erythema on each side of the face. Next, we will measure the surface area of the face with one Fraxel 1927nm nonablative fractionated laser treatment and treat the face with a fluence of 20 mJ and treatment level of 7-11. The following areas will be treated in this order: right forehead, left forehead, left cheek, right cheek, nose, perioral area. After the procedure, we will have them take an electronic RedCap survey on an iPad to determine pain associated with procedure. The physician will also assess for systemic symptoms of lidocaine toxicity. Then, the patient will apply triamcinolone 0.1% ointment for 1 week with vinegar soaks, vaniply, and gentle skin care.

As part of the division of dermatologic surgery procedure protocol, patient will be contacted on post procedure day 1. They will be asked how they are doing, if they have any questions about wound care instructions, pain or blistering as part of standard procedure. Then, in addition to that, we will ask their 1 hour post procedure pain level on a scale of 1-10 for each side of the face”

The following is a patient (70kg female) scenario to ensure safe levels of lidocaine.

We will assume a facial surface area of 300 cm². If half of that (150 cm²) is covered with 7.5 mg lidocaine 2.5%/ prilocaine 2.5% (EMLA Cream) under occlusion for 60 minutes, the lidocaine absorption would be (0.045*150*1) 6.75 mg. The other half of the face would be covered with 2.5 g of Lidocaine 23% / tetracaine 7% ointment, which would cause around 62.1 mg of lidocaine to be absorbed (0.414*150*1). If she was 70 kg, this would be well under the maximum dose (315 mg).

Subject Information

Target accrual: 32

Subject population (children, adults, groups): Adults

Inclusion Criteria:

- a. Male or Female in general good health 18 years of age or older undergoing fraxel laser treatment
- b. Fitzpatrick skin type I-IV with at least mild photodamage of the face by physician discretion
- c. Subject has completed an appropriately administered informed consent process which includes signing the IRB approved consent form
- d. Willingness to have facial exams and digital photos performed of the face
- e. Female patients will be either of non-childbearing potential defined as:
 1. Having no uterus
 2. No menses for at least 12 months.

Or;

(WOCBP) women of childbearing potential must agree to use an effective method of birth control during the course of the study, such as:

1. Oral contraceptive pill, injection, implant, patch, vaginal ring, intrauterine device
2. Intrauterine coil
3. Bilateral tubal ligation
4. Barrier method used with an additional form of contraception (e.g., sponge, spermicide or condom)
5. Abstinence (If practicing abstinence must agree to use barrier method described above (4) if becomes sexually active).
6. Vasectomized partner (Must agree to use barrier method described above (4) if becomes sexually active with non-vasectomized).

Exclusion Criteria:

- a. Presence of incompletely healed wound or active skin disease within in treatment area
- b. Pregnant, planning pregnancy or breastfeeding during the course of the study
- c. Individuals who have ablative laser within 6 months; non ablative lasers, facial peels, or dermabrasion within 1 month
- d. Individuals with known allergies or sensitivities to any of the ingredients of any topical products being used in this study (a list of the products with active and excipients will be provided below)
- e. Subjects with any pre-existing medical or psychological condition which, in the opinion of the investigator, would put them at increased risk due to study treatment or participation
- f. Subjects who are unable to comprehend the study consent document or provide full written consent

- g. Subjects who have taken isotretinoin within 3 months or systemic corticosteroids within 1 month.
- h. Subjects with history of severe cardiovascular disease, kidney disease, liver disease, uncontrolled diabetes, uncontrolled seizures, immunosuppression.

Biospecimens

There will be no collection of biospecimens

Review of medical records, images, specimens

Check all that apply (data includes medical records, images, specimens).

☐ Only data that exists before the IRB submission date will be collected.

Date Range for Specimens and/or Review of Medical Records:

Examples: *01/01/1999 through 12/31/2015*, or all records through *mm/dd/yyyy*.

Note: The Date Range must include the period for collection of baseline data, as well as follow-up data, if applicable.

☒ The study involves data that exist at the time of IRB submission **and** data that will be generated after IRB submission. Include this activity in the Methods section.

Examples

- The study plans to conduct a retrospective chart review and ask subjects to complete a questionnaire.
- The study plans to include subjects previously diagnosed with a specific disease and add newly diagnosed subjects in the future.

☐ The study will use data that have been collected under another IRB protocol. Include in the Methods section and enter the IRB number from which the research material will be obtained. *When appropriate, note when subjects have provided consent for future use of their data and/or specimens as described in this protocol.*

Enter one IRB number per line, add more lines as needed

☐ Data ☐ Specimens ☐ Data & Specimens _____

☐ Data ☐ Specimens ☐ Data & Specimens _____

☐ Data ☐ Specimens ☐ Data & Specimens _____

Data Analysis

Power Statement: Assuming a mean of paired differences of 1.25 on the VAS, a standard deviation of paired differences of 2.3, and a significance level of 5%, we would need 32 patients to achieve at least 80% power using a two-sided paired t-test.

Data Analysis Plan: The mean pain scale from each topical anesthetic will be compared using t-tests.

Endpoints

Primary: To compare the efficacy of lidocaine 23% / tetracaine 7% ointment and lidocaine 2.5%/ prilocaine 2.5% cream in reducing self-reported pain after laser treatment.

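### The trial is labelled double-blinded, but its Methods leave the patient, who alone rates the primary pain outcome, aware of which product is on which side

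*Combined protocol and SAP*

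**What the plan says.** The title page opens with "Prospective, Randomized, Double-blinded, Split-face Study Comparing Efficacy of", and the Study Title field under General Study Information repeats the double-blind claim.

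The Methods paragraphs under Study Design and Methods are the only account of how the products are given:

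- Ointment side: "We will randomly assign half of the face to be applied with 2.5 g of lidocaine 23% / tetracaine 7% ointment without occlusion". The ointment is "applied to the other half of the face by the patient, given that it is their own outside prescription".
- Cream side: "the other half of the face with 7.5 g lidocaine 2.5%/ prilocaine 2.5% cream with occlusion for 60 minutes", and "Lidocaine 2.5%/ prilocaine 2.5% cream will be applied to half the face by nursing staff and occluded".

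After 60 minutes both products are washed off and the face is cleansed. The patient then completes a survey on burning and itching for each side, and physicians grade erythema for each side. After the laser the patient completes a second survey, on pain. On the next day the patient is asked to recall, for each side, the pain one hour after the procedure. The primary endpoint compares the two products "in reducing self-reported pain after laser treatment".

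The documents mention no matched vehicle or container, sham occlusion, named blinded role, restriction on who sees the application, or check of blinding.

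**The concern.** Double-blinding is a claim about validity, and readers will give the result more credit because of it. Here the Methods contradict it for the person whose rating is the primary outcome. If patients expect one product to work better, that expectation enters each within-patient pain difference.

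The split-face design does not protect against this. Randomising the side balances things that belong to the side, such as the fixed order in which facial areas are treated. Pairing removes differences between patients. Expectation travels with the product, so neither removes it, and washing the products off does not remove what the patient knows. The planned t-test cannot separate such a shift from a drug effect.

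There are two lesser issues. Nothing stops the physicians who grade erythema from knowing the allocation. The applicator (patient or nurse) is also completely aligned with the product, so any effect of who applied it cannot be told apart from the product effect.

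**Working it through.** **Step 1. Set the label against the procedures.**

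| Feature | Ointment side | Cream side | Visible to patient? |
|---|---|---|---|
| Applied by | Patient, from own prescription | Nursing staff | Yes |
| Occlusion | None | 60 minutes | Yes |
| Form and amount | Ointment, 2.5 g | Cream, 7.5 g | Yes |

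The first row settles the matter on its own: someone applying their own prescribed product knows where it is.

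**Step 2. See which outcomes this reaches.** Pain after the laser (primary), burning and itching, and the next-day recall of one-hour pain are all rated by the patient. Erythema is rated by physicians whose masking is not described. Systemic toxicity symptoms are also assessed by the physician, but they do not belong to one side of the face.

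**Step 3. Reproduce the plan's own figure.** Inputs from the Power Statement under Data Analysis: mean paired difference 1.25, SD of differences 2.3, two-sided 5% level, paired t-test, 32 patients for at least 80% power.

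- Standard error = 2.3/√32 = 0.4066.
- Noncentrality = 1.25/0.4066 = 3.07 on 31 degrees of freedom.
- Exact noncentral-t power = 84.6%.

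The smallest number reaching 80% is 29 (80.7%; 28 gives 79.2%). So 32 is not the minimum, but it meets the stated target with a small margin. The sample size is not in dispute here. The 95% confidence interval half-width is 2.04 × 0.4066 = 0.83 points.

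**Step 4. Illustrate sensitivity to a shift in the ratings.** The sizes of shift below are assumptions. With a true difference of zero, let knowledge of the side move the mean paired difference by b. The chance of p < 0.05 is the noncentral-t rejection probability with noncentrality b/0.4066 on 31 degrees of freedom.

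| Assumed shift b (VAS points) | Noncentrality | Rejection rate |
|---|---|---|
| 0 | 0 | 5% |
| 0.25 | 0.61 | 9.2% |
| 0.5 | 1.23 | 22.2% |
| 1.0 | 2.46 | 66.4% |

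**Step 5. Take the opposite direction.** If the true difference were the planned 1.25 and a 0.5-point shift worked against the better product, the apparent difference would be 1.25 − 0.5 = 0.75. Noncentrality becomes 0.75/0.4066 = 1.84, and power falls from 84.6% to 43.2%.

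**The case against.** The strongest reply is that this is a comparison of two regimens. Occlusion of the cream alone is part of the title and the stated aim, and ointment against cream is the research question. On this view the differences explain why masking the patient is hard and are not faults. That stands, and it is a reason to drop the label rather than keep it.

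A second reply is that the label may refer to other parties, such as the physician and an analyst. The documents name no blinded role. Even if they did, the rater of the primary outcome would remain unblinded.

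A third reply is that the illustration rests on chosen values and that the remedy does not change it. Both parts are correct. For any given expectation effect, the rates in the working are the same after the label is corrected, the physician is masked and the applicators are aligned. They show how sensitive the test is. They do not measure this plan's bias or what the fix would gain.

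Some stronger readings are tempting but unsupported:

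- A reader might infer that the result will be biased towards the ointment because patients hold a prescription for it. The documents give no size or direction.
- A reader might infer that an untrained patient will cover the skin unevenly. The Methods do not say whether the patient is instructed or supervised, and they fix the amount for each side. Only the alignment of applicator with product is established.
- A reader might infer that the physician watches the application. The documents only fail to prevent it.
- A reader might infer that nursing staff could simply apply both products. The protocol gives a reason why the patient applies the ointment, so this cannot be assumed to be open to the sponsor.

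**Conclusion.** The point holds. The double-blind description is contradicted by the protocol's own Methods, and the contradiction reaches the primary outcome. It follows from the text alone and depends on no calculation. The label must be corrected.

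The size of any resulting bias is unknown. The illustrative figures assume 32 analysed patients, an SD of differences of 2.3, a paired analysis and a constant shift. Under those assumptions a shift of half a point, well below both the planned 1.25 and the 0.83 half-width, is enough to matter in either direction: about 22% false rejections if there is no true difference, or about 43% power if it opposes a true difference of 1.25.

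The documents do not support saying that the comparison is invalid, that the bias favours a particular product, or that the physician is in fact unblinded. Unblinded self-rating of pain is a limitation of the design as described, and it remains after every step of the fix.

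**What to change.** 1. **Correct the label.** Remove the double-blind claim from the title page, the Study Title field and the report. Describe the trial as randomised and split-face with patients not blinded. Report unblinded self-rating of pain (and of burning and itching) as a limitation that the steps below do not remove.
2. **Mask the erythema grading.** Have nursing staff hold the side allocation and complete removal and cleansing of both sides before the physician enters to grade erythema. Call the physician blinded only if this is adopted and written into the Methods. It protects a secondary outcome, not the primary one.
3. **Optional: reduce the confounding of applicator with product**, for example by nurse-supervised application on both sides. First reconcile the source of the ointment: the randomisation sentence in the Methods mentions compounding by the institution's own pharmacy, possibly for both products, while a later sentence in the same paragraph calls the ointment the patient's own outside prescription. Who may apply it could depend on the answer.

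The cost of the first two steps is a less favourable blinding label, some rewording of the title and Methods, and a small change in the order in which existing staff enter the room. The optional third step would also take nursing time for supervision. No extra visits are needed.

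### A side term and a balanced side allocation would be a nearly free improvement: the laser order is fixed by side and the t-test, though valid, does not use side

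*Combined protocol and SAP*

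**What the plan says.** Under Study Design and Methods, side is the randomised factor: "We will randomly assign half of the face to be applied with 2.5 g of lidocaine 23% / tetracaine 7% ointment without occlusion", with the cream going on the other half. No allocation ratio, blocking or other right/left balancing is described. The same section sets one treatment sequence for every patient: "The following areas will be treated in this order: right forehead, left forehead, left cheek, right cheek, nose, perioral area".

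Under Data Analysis, the Data Analysis Plan is one sentence: "The mean pain scale from each topical anesthetic will be compared using t-tests". The Power Statement makes clear that the test is paired and gives its inputs: "Assuming a mean of paired differences of 1.25 on the VAS", "a standard deviation of paired differences of 2.3", a 5% significance level, and the result "we would need 32 patients to achieve at least 80% power using a two-sided paired t-test". Subject Information repeats the number: "Target accrual: 32". Neither Data Analysis statement mentions side, facial area or treatment order.

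**The concern.** Among the four areas that belong to one side, the right side always has the first (forehead) and the last (cheek). Within each area the order is never reversed: right forehead precedes left, and left cheek precedes right. A first-area effect, a non-linear order effect or a systematic anatomical difference would make one side hurt more regardless of product.

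Such a difference enters the ointment-minus-cream score with a plus sign when the ointment is on the right and a minus sign when it is on the left. A test that does not use side counts this as noise. If the two allocations are not equally frequent, part of it also remains in the observed mean difference. At stake are some precision and the size of the reported estimate in the one trial that is run.

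**Working it through.** **Inputs from the documents.** Mean paired difference 1.25, SD of paired differences 2.3, two-sided 5% level and N = 32 (Power Statement, Subject Information). Side is randomised by an unstated method, and the laser order is fixed (Methods).

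**Assumptions.** The documents give no right-left pain difference, so I write it as p and take 0.25, 0.5, 0.75 and 1.0 VAS points. Split probabilities assume simple 1:1 randomisation.

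**Step 1: the plan's own figure.** Exact paired t-test power (noncentral t, n − 1 df, noncentrality 1.25·√n/2.3) is 79.2% at n = 28, 80.7% at n = 29 and 84.6% at n = 32. The smallest n for 80% is therefore 29. The stated 32 is slightly more than required and meets the at-least-80% claim.

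**Step 2: order balance.** The four lateral areas run R, L, L, R. Mean position is (1 + 4)/2 = 2.5 on the right and (2 + 3)/2 = 2.5 on the left, so a linear trend over these positions cancels.

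**Step 3: model.** For patient i, D = δ + s·p + e, with s = +1 if the ointment is on the right and −1 if on the left.

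- Without a side term, under simple randomisation, SD(D) = √(SD_e² + p²), tested on 31 df.
- With a side term and a 16:16 split, the SD is SD_e, tested on 30 df.
- Given the observed split, the unadjusted mean moves by p·(n_R − n_L)/32. At 20:12 this is p·8/32 = p/4.

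**Step 4: results at N = 32.** In columns 2 to 4 the 2.3 excludes p, so SD_e = 2.3. In columns 5 and 6 the 2.3 includes p, so SD_e = √(5.29 − p²), and the unadjusted power is 84.6% throughout.

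| p | SD without side term | Power without side term | Power with side term, 16:16 | SD_e if 2.3 includes p | Power with side term, 16:16 | Shift at 20:12 |
|---|---|---|---|---|---|---|
| 0.25 | 2.31 | 84.1% | 84.5% | 2.29 | 84.9% | 0.06 |
| 0.50 | 2.35 | 82.9% | 84.5% | 2.25 | 86.2% | 0.13 |
| 0.75 | 2.42 | 80.8% | 84.5% | 2.17 | 88.2% | 0.19 |
| 1.00 | 2.51 | 78.0% | 84.5% | 2.07 | 91.0% | 0.25 |

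With p = 0 the side term costs 0.1 points of power (84.6% to 84.5%). N = 32 keeps 80% power up to a total SD of about 2.44. That corresponds to p of about √(2.44² − 2.3²) ≈ 0.8 when 2.3 excludes p.

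**Step 5: chance imbalance.** With Binomial(32, ½), a split of 20:12 or worse has probability 21.5%, and 22:10 or worse 5.0%.

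**Step 6: type I error of the plain paired t-test (simulation, 100,000 runs).**

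| Allocation | p = 0.5 | p = 1.0 |
|---|---|---|
| Simple randomisation | 4.9% | 5.0% |
| Fixed 16:16 | 4.5% | 3.3% |
| Given a 20:12 split | 5.5% | 6.6% |

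The planned test holds its level under simple randomisation. If the split is balanced but the side term is left out, the test becomes conservative. Its simulated power at p = 1.0 and 16:16 is 79.7%, against 84.5% with the term.

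**The case against.** The strongest reply is that nothing here is wrong. Side is randomised, so the estimate is unbiased over randomisations and the paired t-test keeps its 5% level. A shift at 20:12 is conditional on that split, and the ordinary standard error already allows for it. Leaving out a precision covariate is a choice. All of this stands, and it is why the point is an improvement and not a defect.

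A reader might infer that the fixed sequence biases the product comparison. The documents do not support that. The sequence favours neither product, its lateral part is counterbalanced for a linear trend, and the procedure ends on the nose and perioral area, which the order does not assign to a side. An end-of-procedure effect therefore need not fall on the right cheek.

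A reader might also infer that the trial loses its planned power. That needs a right-left difference above about 0.8 points on top of the 2.3. Since 2.3 is described as the SD of paired differences, it may already contain side variation, and then nothing is lost against plan. A 1-point effect would be 80% of the planned treatment difference (1/1.25), so it is the top of the range and not a central case.

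Two further limits stand. The protocol is silent on how side is randomised, so the 21.5% does not apply if the list is already balanced. And a right/left indicator removes only a systematic mean difference; asymmetry that varies in direction between patients stays in the residual.

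The reply does not give a reason to leave side out: the term costs almost nothing when there is no side effect, and it gains power at 16:16 for every effect size examined.

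**Conclusion.** The point holds as a low-severity improvement. The planned analysis is valid, but it leaves any systematic right-left difference in the error term and, given an uneven split, in the observed estimate. For assumed differences of 0.25 to 0.5 points the precision at stake is small: about 0.3 to 1.6 points of power, whichever way the 2.3 is read. At 1 point it is about 6.5 points of power (78.0% against 84.5%, or 84.6% against 91.0%), with a possible 0.25-point shift at 20:12. The effect sizes and simple randomisation are assumptions; the documents supply neither.

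**What to change.** Make two changes together, and leave the laser sequence as it is.

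1. Allocate side in permuted blocks so that 16 patients have the ointment on the right and 16 on the left, and state this in Methods.
2. In the Data Analysis Plan, prespecify a linear regression of the within-patient ointment-minus-cream pain difference on an indicator for ointment on the right, coded +½ and −½. The intercept, with its 95% CI on 30 df, is the treatment effect.

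Blocking keeps the right-left difference out of the estimate, and the side term takes it out of the error variance. Blocking alone would leave the plain test conservative (4.5% at 0.5 points, 3.3% at 1 point).

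The cost is a blocked allocation list and one degree of freedom, or 0.1 points of power if there is no side effect. No further patients, visits or measurements are needed, because the allocated side must be known anyway to attach each score to a product.
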